# 7.1.4.1 Replacement policy

Patients will not be replaced on study.

However, if a patient is considered as non-evaluable for the per-protocol set (PPS), enrollment of a new patient will be considered if there is less than the required number of evaluable patients.

### 7.1.5 Withdrawal of consent

Patients/legal guardian may voluntarily withdraw assent/consent to participate in the study for any reason at any time. Withdrawal of assent/consent occurs only when a patient/legal guardian:

- Does not want to participate in the study any longer, and
- Does not allow further collection of personal data.

If a patient/legal guardian withdraws assent/consent, the investigator should make a reasonable effort (e.g. telephone, e-mail, letter) to understand the primary reason for the patient/legal guardian decision to withdraw his/her consent and record this information.

Study treatment must be discontinued and no further assessments conducted, and the data that would have been collected at subsequent visits will be considered missing.

Further attempts to contact the patient/legal guardian are not allowed unless safety findings require communicating or follow-up.

All efforts should be made to complete the assessments prior to study withdrawal. A final evaluation at the time of the patient's study withdrawal should be made as detailed in the assessment table.

Novartis will continue to keep and use collected study information (including any data resulting from the analysis of a patient's samples until their time of withdrawal) according to applicable law

For US and Japan: All biological samples not yet analyzed at the time of withdrawal may still be used for further testing/analysis in accordance with the terms of this protocol and of the informed consent form.

For EU and RoW: All biological samples not yet analyzed at the time of withdrawal will no longer be used, unless permitted by applicable law. They will be stored according to applicable legal requirements.

# 7.1.6 Follow up for safety evaluations

All patients must have safety evaluations for at least 30 days after the last dose of study treatment as per Table 7-1, Table 7-2 for LGG crossover patients, or Table 7-3. Data collected should be added to the Adverse Events eCRF and the Concomitant Medications eCRF.

### 7.1.6.1 Post treatment follow up

After discontinuation of study treatment, all patients will be followed for safety for at least 30 days after the last dose of study treatment except in the case of death, loss to follow-up or withdrawal of consent/assent. All patients who discontinue study treatment for reasons other than disease progression, death, lost to follow up, or withdrawal of consent/assent will move into Post Treatment Follow Up phase.

Tumor evaluations during this period will continue as per Table 7-1, Table 7-2 or Table 7-3 until central independently confirmed disease progression by RANO criteria, withdrawal of assent/consent by patient/guardian to tumor status follow-up, or lost to follow-up. Patients who start a new anti-cancer therapy prior to disease progression will continue tumor evaluations following the same above schedule until radiographic evidence of disease progression is centrally confirmed.

Skin examinations should be performed at 3 and 6 months after the last dose of study drug or until the start of a new anti-cancer therapy. Safety assessments including physical exams and

growth/developmental follow up will continue according to Table 7-1, Table 7-2 or Table 7-3 and Section 7.1.6.

Patients who discontinue study treatment due to disease progression by RANO criteria that has been confirmed by central independent assessment, and begin new anti-cancer therapy at EOT will enter Survival follow-up period.

### 7.1.6.2 Survival follow-up

All patients will be followed for survival once they discontinue study treatment and complete protocol required efficacy assessments, and the required skin evaluation per Table 7-1, Table 7-2 for LGG crossover patients or Table 7-3. Survival follow-up assessments will be done every 12 weeks or earlier if a survival update is required to meet safety or regulatory needs. Survival information can be obtained by clinical visits or telephone calls until death, the patient is lost to follow-up, the patient/legal guardian withdraws assent/consent or study discontinuation.

# 7.1.7 Lost to follow-up

For patients whose status is unclear because they fail to appear for study visits without stating an intention to withdraw consent/assent, the investigator should show "due diligence" by contacting the patient, family or family physician as agreed in the informed consent/assent and by documenting in the source documents steps taken to contact the patient, e.g. dates of telephone calls, registered letters, etc. A patient should not be considered lost to follow-up until due diligence has been completed. Patients lost to follow up should be recorded as such on the appropriate Disposition CRF.

# 7.2 Assessment types

# 7.2.1 Efficacy assessments

Tumor response will be assessed locally and centrally based on the Response Assessment in Neuro-Oncology (RANO) criteria for solid tumors (Wen, 2010). The imaging assessment collection plan is presented in Table 7-4. Details of the central review process will be described in the independent review charter by the assigned imaging vendor.

Imaging data will be centrally collected and checked for quality by an imaging vendor designated by Novartis. The decision regarding patient management will remain with the local investigator.

Information regarding prior interventions (e.g. radiotherapy), pre-existing radiographic findings that mimic metastatic disease at baseline/screening, prior and on-study interventions, and cytology results should be transmitted to the imaging vendor for review by an independent medical radiologist. Sites must ensure the data transmitted is consistent with the data entered in the clinical database.

For patients who discontinue treatment for reasons other than documented disease progression, death, lost to follow-up, or withdrawal of consent/assent, tumor assessments must continue to be performed every 16 weeks until documented disease progression, death, lost to follow-up, or withdrawal of consent/assent.

| Procedure a                | Screening         | During Treatment/Follow-up  | End of Treatment |
|---------------------------------------|-------------------|---|------------------|
| Tumor evaluation
Brain MRI         | Mandated          | Every 8 weeks (+/- 7 days) during the first 56 weeks.   | Mandated         |
|                                       |                   | 
 
Every 16 weeks (+/- 7 days) thereafter
while on treatment as well as during
post-treatment follow up.
 
                   |                  |
|                                       |                   | 
 
PR and CR must be confirmed by
repeat assessments performed ≥4
weeks after the criteria for response are
first met.
 
 |                  |
|                                       |                   | 
 
At any time there is suspicion of clinical disease progression.
 
   |                  |
| MRI Spine                             | As clinically ind | licated per investigator discretion   | ·                |
| a Refer to Section 7.2.1.1 |                   |   |                  |

# 7.2.1.1 Baseline imaging assessments

Imaging assessments will be performed at screening/baseline within 28 days of start of treatment (Day -28 to Day -1).

Any imaging assessments already completed during the regular work-up of the patient within 28 days prior to start of treatment, including before signing the study ICF, can be considered as the baseline images for this study. The following assessments are required at screening/baseline:

- Brain MRI Contrast enhanced brain MRI is preferred. However, if MRI contrast is contraindicated, CT with or without contrast is allowed, but highly discouraged.
- MRI spine may be obtained if clinically indicated according to investigator discretion

### Required conditions for baseline tumor assessment

- During screening, patients must have locally determined and centrally confirmed measurable disease at least twice the imaging slice thickness to be used for efficacy assessment
- Patients with only non-measurable lesions are not eligible
- Any potentially measurable lesion that has been previously treated with radiotherapy should be considered as a non-measurable lesion. However, if a lesion previously treated with radiotherapy has clearly progressed since more than 3 weeks from the radiotherapy, it can be considered as a measurable lesion.

Since measurable disease is an eligibility requirement, study sites should send the baseline imaging scans and any required vendor forms to the imaging CRO immediately following scan acquisition during screening. Rapid image transmission to the imaging CRO may be accomplished by transferring the images electronically. The baseline imaging will undergo expedited central review and the results of the central review will be communicated to the site. If the central review determines measurable disease, then the patient can be enrolled in the study. If the central review does not determine measurable disease, the patient should not be enrolled in the study; additional follow-up can be requested.

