#### 5.2 Inclusion criteria

Patients eligible for inclusion in this study have to meet all of the following criteria:

- 1. Male or female between ≥12 months and <18 years of age at the time of signing the informed consent form. Patients under 6 years old must weigh at least 7 kg at the time of enrollment. Patients over 6 years old must weigh at least 10 kg at the time of enrollment.
- 2. **For HGG cohort only:** Relapsed, progressed, or failed to respond to frontline therapy. Frontline therapy is presumed to be optimal surgical approach (biopsy or resection) with radiation and/or chemotherapy.
  - **For LGG cohort only:** Patients with progressive disease following surgical excision, or non-surgical candidates with necessity to begin first systemic treatment because of a risk of neurological impairment with progression.
- 3. Locally determined HGG or LGG as defined by WHO histological classification system, revised 2016 (Appendix 4). For HGG cohort only: Locally confirmed histologic diagnosis of High Grade Glioma (Grade III or IV glioma), including anaplastic pleomorphic xanthoastrocytoma (aPXA) and anaplastic gangliogliomas.
  - **For LGG cohort only**: Locally confirmed histologic diagnosis of Low Grade Glioma (Grade I or II)
- 4. Locally determined and centrally confirmed measurable disease with minimal biperpendicular diameter that must be at least twice the imaging slice thickness to be used for efficacy assessments. (Both local and centrally confirmed results must show measurable disease to meet eligibility)
- 5. *BRAF* V600 mutation-positive tumor as assessed locally, or at a Novartis designated central reference laboratory if local *BRAF* V600 testing is unavailable.
- 6. Tumor tissue must be available and subsequently provided to Novartis for central confirmatory testing of *BRAF* mutational status (HGG and LGG cohort), and for HGG histopathology (HGG cohort).
- 7. Performance score of  $\geq$ 50% according to the Karnofsky/Lansky performance status scale.
- 8. Females of child-bearing potential must be willing to practice acceptable methods of birth control. Additionally, females of childbearing potential must have a negative serum pregnancy test within 28 days prior to day 1.
- 9. Must have adequate bone marrow function per central or local lab in the absence of growth factor support and is defined as:
  - Absolute neutrophil count (ANC) ≥1000/μL;

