#### 5.3 Exclusion criteria

Patients eligible for this study must not meet any of the following criteria:

- 1. Malignancy OTHER than BRAF V600 mutant HGG or LGG.
- 2. Previous treatment with dabrafenib or another RAF inhibitor, trametinib or another MEK inhibitor, or ERK inhibitor.
- 3. HGG patients: Cancer therapy (chemotherapy with delayed toxicity, immunotherapy, biologic therapy, vaccine therapy) or investigational drugs within 3 weeks preceding the first dose of study treatment. LGG patients: Any systemic anticancer therapy (chemotherapy, immunotherapy, biologic therapy, or vaccine therapy) or investigational drugs prior to enrollment.
- 4. HGG patients: Radiotherapy to CNS glioma lesions within 3 months prior to first dose of study treatment, unless there is clear evidence of radiologic progression outside of the field of radiation. LGG patients: Radiotherapy to CNS glioma lesions at any point prior to enrollment.
- 5. History of malignancy with confirmed activating RAS mutation or with *BRAF* fusion such as BRF-KIAA1549 or with known diagnosis of NF1. Note: Prospective RAS testing is not required. However, if the results of previous RAS testing are known, they must be used in assessing eligibility.
- 6. Current use of a prohibited medication or herbal preparation or requires any of these medications during the study. See Section 6.4 for details.
- 7. Unresolved toxicity greater than NCI CTCAE v 4.03 grade 2 from previous anti-cancer therapy, including major surgery, except those that in the opinion of the investigator are not clinically relevant given the known safety/toxicity profile of the study treatment (e.g., alopecia and/or peripheral neuropathy related to platinum or vinca alkaloid based chemotherapy).
- 8. History of allergic reactions attributed to compounds of similar chemical or biologic composition to dabrafenib, trametinib and their excipients. For LGG patients only: history

- of allergic reactions or contraindications to the use of carboplatin or vincristine (refer to local product label or SmPC).
- 9. Autologous or allogeneic stem cell transplant within 3 months prior to the first dose of study treatment [NOTE: patients with evidence of active graft versus host disease are excluded regardless of elapsed time].
- 10. History or current diagnosis of cardiac disease indicating significant risk of safety for patients participating in the study such as uncontrolled or significant cardiac disease, including any of the following:

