#### Response definitions for HGG:

- Complete response (CR): Complete disappearance of all enhancing measureable and nonmeasureable disease on contrast enhanced MRI scan sustained for at least 4 weeks, no new lesions, and stable or improved nonenhancing (T2/FLAIR) lesions. In addition, patient must be off steroids or only on physiologic replacement doses. In the absence of a confirming scan 4 weeks later, this response will be considered only stable disease.
- Partial response (PR): Greater than or equal to a 50% reduction, compared to baseline, in the sum of products of the perpendicular diameters for all measurable lesions for at least 4 weeks, no progression of nonmeasureable disease, no new lesions, and stable or improved nonenhancing (T2/FLAIR) lesions. In addition, patient must be on a corticosteroid dose not greater than the dose at the time of baseline scan and be stable or improving clinically. In the absence of a confirming scan 4 weeks later, this response will be considered only stable disease.
- Progressive Disease (PD): Greater than or equal to a 25% increase in sum of the products of perpendicular diameters of enhancing lesions (compared with baseline if no decrease) on stable or increasing doses of corticosteroids, OR a significant increase in T2/FLAIR

nonenhancing lesions on stable or increasing doses of corticosteroids compared with baseline scan or best response after initiation of therapy, not due to comorbid events, OR the appearance of any new lesions, OR clear progression of nonmeasurable lesions, OR definite clinical deterioration not attributable to other causes apart from tumor, or to decrease in corticosteroid dose. Failure to return for evaluation as a result of death or deteriorating condition should also be considered as progression.

• Stable disease: If patient does not qualify for CR, PR, or PD and has stable nonenhancing (T2/FLAIR) lesions on same or lower doses of corticosteroids compared with baseline scan and clinically stable status. In the event that the corticosteroid dose was increased for new symptoms and signs without confirmation of disease progression on neuroimaging and subsequent follow-up imaging shows that this increase in corticosteroid dose was required because of disease progression, the last scan considered to show stable disease will be the scan obtained when the corticosteroid dose was equivalent to the baseline dose.

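### An irradiated lesion can become measurable after 3 weeks, while HGG exclusion 4 refuses in-field progression for 3 months; the two windows are not reconciled, so in-field shrinkage can reach the single-arm ORR by two limited routes

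*Protocol*

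**What the plan says.** Section 7.2.1.1 (required conditions for baseline tumor assessment) sets a default: "Any potentially measurable lesion that has been previously treated with radiotherapy should be considered as a non-measurable lesion". It then allows an exception where the lesion "has clearly progressed since more than 3 weeks from the radiotherapy, it can be considered as a measurable lesion". The exception does not depend on where the lesion lies relative to the radiation field.

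Section 5.3, exclusion 4, for HGG patients, bars "Radiotherapy to CNS glioma lesions within 3 months prior to first dose of study treatment". The interval is counted back from first dose, and only out-of-field progression lifts the bar.

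Inclusion 2 in Section 5.2 makes prior irradiation likely in this cohort: "Frontline therapy is presumed to be optimal surgical approach (biopsy or resection) with radiation and/or chemotherapy". LGG patients with any earlier radiotherapy to CNS glioma lesions are excluded, so the point concerns HGG only.

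Baseline imaging may be up to 28 days before treatment starts (Section 7.2.1.1). In Appendix 3 (Section 14.3), an HGG partial response needs a fall of at least half "in the sum of products of the perpendicular diameters for all measurable lesions for at least 4 weeks". Appendix 3 makes no separate provision for irradiated lesions. The Evaluable Set (Section 10.1.6.1) asks for centrally confirmed measurable disease and does not mention radiotherapy.

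**The concern.** For a patient within 3 months of radiotherapy, exclusion 4 does not accept growth inside the field as grounds for entry. The measurability rule can accept the same growth as target disease from 3 weeks. Any lesion accepted as measurable joins the baseline sum from which response is computed.

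The HGG primary endpoint is ORR in a single arm, read against historical rates. Section 2.2 defends ORR as a direct measure of treatment effect that natural history does not affect. That defence requires baseline lesions to be tumour whose shrinkage can be credited to the study drugs. If an in-field lesion shrinks for another reason, no concurrent arm reveals it, and the false response also feeds duration of response and time to response. The repeat analysis on the Evaluable Set (Section 10.4.4) would keep these patients, because they have centrally confirmed measurable disease.

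**Working it through.** **Inputs.** N = 40, single arm; futility criterion met at 4 or fewer responders of 16; reference rates 20% (95% CI) and 32% (80% CI), all from Sections 10.4.2, 10.7.1 and 10.8.1. Windows of 3 weeks and 3 months and the 28-day baseline period are as above. I take 3 months as 91 days.

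**1. The plan's own figures.** The Clopper-Pearson lower limit is the α/2 quantile of Beta(x, n − x + 1).
- 14/40: lower 95% limit 20.6%. Table 10-3 gives 20.6% for 14 and 18.6% for 13, so 14 is the smallest count that excludes 20%.
- 18/40: lower 80% limit 34.1%; 17/40: 31.7%. So 18 is the smallest count that excludes 32%.
- Two-stage success at true ORR 20%: the sum over x = 5 to 16 of P(X16 = x) × P(X24 ≥ 14 − x) = 1.57%. Futility is 79.82% and neither outcome 18.60%. Table 10-4 prints 1.6, 79.8 and 18.6.

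The plan's figures are reproduced.

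**2. The two windows side by side.**

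| | Lesion rule (7.2.1.1) | Exclusion 4 (5.3) |
|---|---|---|
| Acts on | lesion | patient |
| Interval | more than 3 weeks | 3 months |
| Counted | from radiotherapy to progression | back from first dose |
| In-field growth | accepted if clear | does not lift the bar |

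A patient irradiated within 3 months whose only progression is in-field cannot enter. Two routes remain.

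**3. Route (a): entry through the out-of-field exception.** The patient may also have an in-field lesion that grew after week 3, and it joins the baseline sum. Let A be the out-of-field area and B the in-field area at baseline. If A does not change, a partial response needs a fall of at least 0.5 × (A + B), all from B. Since B can fall by at most B, this requires B ≥ A.

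Hypothetical case: A = 15 × 15 = 225 mm², and B = 25 × 25 = 625 mm² falling to 10 × 15 = 150 mm². The sum goes from 850 to 375, a fall of 475/850 = 56%. The limit for response is 425, so the response is lost once A exceeds 425 − 150 = 275 mm², which is growth of 50/225 = 22%. Out-of-field disease therefore dilutes this route strongly.

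**4. Route (b): radiotherapy just over 3 months before first dose.** Exclusion 4 no longer applies. With a Day −28 scan, baseline falls 91 − 28 = 63 days, or 9 weeks, after radiotherapy. In-field growth dated between 3 weeks and that scan can make the lesion measurable and can satisfy inclusion 4 on its own.

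**5. What one false responder does.** It adds 1/40 = 2.5 points at the primary analysis and 1/16 = 6.25 points at the interim, where 4/16 meets the futility criterion and 5/16 does not. If k patients are certain false responders, the chance of at least 14/40 is P(Bin(40 − k, 0.20) ≥ 14 − k), ignoring the interim: 1.94% for k = 0, 3.55% for k = 1 and 6.23% for k = 2.

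**6. Illustration under assumptions.** The documents give neither the share s of patients with such a lesion nor the chance q that its shrinkage alone produces a response. Assume s = 5–20% and q = 25–50%. Apparent ORR = π + (1 − π)sq.
- π = 20%: from 0.20 + 0.80 × 0.05 × 0.25 = 21% to 0.20 + 0.80 × 0.20 × 0.50 = 28%, or 0.4 to 3.2 extra responses per 40. The chance of passing 14/40 with the interim goes from 1.6% to between 2.4% and 17.3%.
- π = 32%: the chance of passing 18/40 with the interim goes from 5.7% to between 7.2% and 25.3%.

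These ranges show sensitivity only. They do not estimate the bias.

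**The case against.** A reader might call this a contradiction. The text does not support that: exclusion 4 decides who enters, Section 7.2.1.1 decides what is measured, and both can be applied together. Exclusion 4 gives no reason for its interval and says nothing about measurability.

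A reader might also conclude that resolving radiation change will be scored as response. The documents never describe irradiated enhancement settling by itself. The inference rests on their own default that irradiated lesions are not measurable and on exclusion 4 not accepting in-field progression.

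The safeguards are real. The most direct route is closed. The exception asks for clear progression, measurability must be confirmed centrally before enrolment, radiotherapy history goes to the independent reader (Section 7.2.1), and response must be confirmed at least 4 weeks later. Partial response also needs stable or improved non-enhancing lesions, no new lesions, no progression of non-measurable disease, no steroid increase above baseline and no clinical worsening. Review details are left to an imaging charter that is not at hand. By route (b), growth that has already settled before the baseline scan does not count.

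These points narrow the gap without closing it. The central reader applies a rule that admits the lesion, and confirmation does not separate drug effect from other lasting shrinkage.

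Nor can a number of doubtful responses be inferred, since no frequency is given. Section 10.8.1 calls the 20% and 32% levels illustrative and sets no success threshold, and sensitivity to one responder at a cut-off is common to any binomial rule.

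**Conclusion.** The point holds as an unreconciled mismatch that opens two limited routes into the HGG primary endpoint. Its direction is clear: shrinkage of such a lesion from any cause other than the study drugs would raise ORR, and the single arm cannot show it. Its size is unknown. The only firm figure is 2.5 points per false responder among 40, where that patient would not otherwise have responded. The assumed range in the working shows that a few such patients could matter near the illustrative cut-offs, not that they exist. The conclusion assumes that the imaging charter does not already settle the matter. It is a low-cost improvement and does not by itself undermine the HGG result.

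**What to change.** - Reconcile the measurability exception in Section 7.2.1.1, and the imaging charter, with the exclusion 4 interval, so that the same in-field change is not refused for entry and accepted for response measurement. Which clinical interval is right is not proposed here.
- Pre-specify a sensitivity analysis of HGG ORR by central review for in-field lesions whose progression was dated within 3 months of radiotherapy, the protocol's own interval. One version removes the affected patients; the other treats the lesions as non-measurable and recomputes the sum. Report how many patients are affected.

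The analysis uses radiotherapy dates and scans already collected (Sections 7.1.2.3 and 7.2.1). A new entry condition, such as requiring a measurable lesion outside the field, is not needed: by the Amendment 5 note, 26 of about 40 HGG patients had already been treated, and such a condition would shrink an already rare population.

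The cost is a protocol and charter clarification, a little extra analysis, and possibly a lost target lesion for a few later HGG candidates. Because most patients entered under the present rule, the sensitivity analysis matters more than the wording change.
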